5 POPULATION

5.1 Definitions

Patients officially enter the Screening Period by signing the main informed consent either directly or via a legally authorized representative wherever permitted by local law.

An enrolled patient is one who has been deemed eligible without waiver of patient population criteria and has been assigned to a treatment group.

5.1.1 Informed Consent and Screening Period

5.1.1.1 Pre-Screening Period

Pre-screening period is defined from the signing of the pre-screening informed consent, to obtaining the IDH mutational status report, or to withdrawal of consent. Patients who have already tested positive for mIDH may enter the Screening Period directly.

Patients who fail pre-screening will have the following information recorded: demographic information, disease diagnosis, mIDH status results (if available), and reason for pre-screening failure.

5.1.1.2 Screening Period

Screening Period is defined as the period from main study consent until the first dose of HMPL-306 (Part 1: Day 1 of PK week, Part 2: C1D1).

A screen failure is a consented patient who has been deemed ineligible on the basis of 1 or more eligibility criteria or who has withdrawn consent prior to treatment. Screen failures may be rescreened.

Before informed consent is obtained, examinations for standard treatment performed within 28 days before planned C1D1 (60 days for ophthalmologic exams) can be used to replace assessments required for eligibility, except for assessments that need to be performed 7 days prior to study drug administration in the dose expansion part as specified in [Table 2](#). For patients enrolled in dose escalation, all screening assessments must be completed before study drug administration on Day 1 of PK week.

5.1.1.3 Rescreening

Patients who cannot complete the procedures within the screening window may be rescreened, and certain screening procedures may not need to be repeated, including certain procedures that were obtained as part of the patient's standard care prior to providing informed consent for this study, with documented sponsor approval.

Individuals who do not meet the criteria for participation in this study (screen failure) may be rescreened, only after discussion with and permission from the HUTCHMED clinical research physician or designee.

Patients may be eligible for rescreening up to 2 times in any of the following circumstances:

- Patients who have become eligible to enroll in the study as the result of a protocol amendment.

- Patients whose status has changed such that the eligibility criterion that caused the patient to screen fail would no longer cause the patient to screen fail again.
- Patients who complete screening and meet all inclusion and exclusion requirements but are unable to be enrolled due to extenuating circumstances (such as severe weather or child illness).

Each time rescreening is performed, the individual must sign a new informed consent form (ICF) and will be assigned a new identification number.

5.2 Inclusion Criteria

Patients may be enrolled in this study only if they satisfy all the following criteria:

1. Patients aged ≥ 18 years.
2. Patients with advanced relapsed, refractory, or resistant hematological malignancies, as defined below:

Part 1:

- a. Patients with documented IDH mutation per local or institutional next generation sequence (NGS).
- b. Patients must be refractory to or intolerant of established therapies known to provide clinical benefit.
- c. Patients who have received prior IDH inhibitor treatment may be enrolled in the escalation part of the protocol.

Part 2:

- a. Patients with documented IDH mutation of any of these subsets: IDH1 (R132C), IDH1 (R132H), IDH2 (R140Q), and IDH2 (R172K), including co-mutations and any combination thereof per local or institutional NGS.
- b. Patients must have received at least 1 prior line of therapy. An established standard of care with proven benefit for which the patient is eligible, must not be available at the time of enrollment.
- c. Patients with R/R AML must have progressed on prior IDH treatment. Patients with AML must not have standard therapeutic options available (including IDH inhibitors where approved) and have the following:
 - i. Relapsed AML unsuitable for intensive chemotherapy or venetoclax-based regimen or target agents;
 - ii. Primary refractory AML unsuitable for intensive chemotherapy or venetoclax-based regimen or target agents.
- d. Patients with relapsed/refractory AML/ include the following:
 - i. Subjects who relapse after transplantation;
 - ii. Subjects in second or later relapse;
 - iii. Subjects who are refractory to initial induction or re-induction treatment.

3. Patients must agree to bone marrow aspiration or biopsy performed before and during the treatment as specified in [Appendix 1](#) (Part 1) or [Appendix 2](#) (Part 2).
4. Patients must have an Eastern Cooperative Oncology Group (ECOG) Performance Status (PS) of 0 to 2 ([Appendix 3](#)).

5. Patients must have adequate hepatic function as evidenced by: aspartate aminotransferase (AST), and alanine aminotransferase (ALT), $\leq 3.0 \times$ upper limit of normal (ULN), unless considered due to leukemic disease and serum total bilirubin $\leq 1.5 \times$ ULN.
6. Patients must have creatinine clearance ≥ 60 mL/min as estimated by the Cockcroft-Gault formula.
7. Patients must recover to Grade <1 from any clinically relevant toxic effects of prior surgery, radiotherapy, or other therapies intended for the treatment of cancer.
8. Female patients of childbearing potential must have a negative serum pregnancy test within 7 days of study drug administration.
NOTE: Postmenopausal is defined as at least 12 months of amenorrhea without alternative medical cause.

9. Male patients with partners of childbearing potential must agree to use a condom, and female patients of childbearing potential must agree to use highly effective form(s) of contraception that result in a low failure rate (<1% per year) when used consistently and correctly starting in the Screening Period, continuing throughout the entire study period, and for 30 days after taking the last dose of study drug. Such methods include combined hormonal contraception (estrogen/progestogen) associated with the inhibition of ovulation (oral, intravaginal, or transdermal), progestogen-only hormonal contraception associated with inhibition of ovulation (oral, intravaginal, or implantable), intrauterine device, intrauterine hormone-releasing system, bilateral tubal ligation, vasectomized partner, or sexual abstinence, if this is the normal and preferred lifestyle. Any hormonal method of highly effective contraception should always be combined with a condom because HMPL-306 may reduce their effectiveness.

5.3 Exclusion Criteria

Patients are not eligible for enrollment into this study if they meet any of the following criteria:

1. Patients who have undergone hematopoietic stem cell transplantation (HSCT) within 60 days of the first dose of HMPL-306, or with clinically significant active graft-versus-host disease
2. Patients who received an investigational agent <14 days prior to their first day of study drug administration
3. Patients who are pregnant or breastfeeding
4. Patients with an active severe infection or with an unexplained fever $>38.3^{\circ}\text{C}$ during screening visits or on their first day of study drug administration (at the discretion of the Investigator, patients with an infection that is controlled with appropriate therapy are eligible); see [Appendix 4](#) for coronavirus disease 2019 (COVID-19) risk assessment.
5. Patients with New York Heart Association Class III or IV congestive heart failure, left ventricular ejection fraction $<40\%$ by echocardiogram (ECHO), or a multigated acquisition (MUGA) scan within approximately 28 days of C1D1 ([Appendix 5](#))
6. Patients with a history of myocardial infarction within the last 6 months of screening
7. Patients with a known unstable or uncontrolled angina pectoris
8. Patients with congenital long QT syndrome or a known history of severe and/or uncontrolled ventricular arrhythmias
9. Electrocardiogram without any clinically significant findings, and for QT interval corrected for heart rate using Fridericia's formula (QTcF - interval from the start of the Q

wave to the end of the T wave [QT] corrected for heart rate using Fridericia's formula) interval >470 ms (for women) and >450 ms (for men), or other factors that increase the risk of QT prolongation or arrhythmic events and per the investigator's assessment

10. Patients taking medications that are known to prolong the QT interval ([Appendix 6](#)) NOTE: Patients may participate if medications are changed to acceptable alternatives
11. Patients with known active/untreated infection with human immunodeficiency virus (HIV), active hepatitis B virus (HBV), or hepatitis C virus (HCV)
12. Patients with immediately life-threatening, severe complications of leukemia such as uncontrolled bleeding, pneumonia with hypoxia or shock, and/or disseminated intravascular coagulation
13. Patients taking medications that can inhibit or induce **CCI** and/or **CCI** ([Appendix 7](#)) within 1 week or 5 half-lives (whichever is longer) before the start of study treatment
14. Patients who received small-molecule or large-molecule (such as antibody-based drug) drugs in previous clinical studies for <2 weeks, or <4 weeks, respectively, from the time of start of the study treatment to the last use
15. Patients with clinically significant, or severe gastrointestinal disease or condition that investigators suspect may affect drug absorption, including, but not limited to, active gastric and duodenal ulcers, ulcerative colitis and other digestive disease, gastrointestinal tumor with active bleeding, or other gastrointestinal conditions that may cause bleeding or perforation, by investigator's discretion
16. Patients with a clinically significant liver disease or condition such as Gilbert syndrome, and at the discretion of the investigator, may affect drug metabolism
17. Patients with a medical condition, physical examination finding, or clinical laboratory finding that, in the Investigator's opinion, contraindicates the use of an investigational drug or that may affect the interpretation of the results or renders the patient at high risk from treatment complications
18. Patients with a known hypersensitivity to HMPL-306 or to any of its excipients
19. Patients with presence of second primary malignant tumors within the last 2 years, with the exception of the following, if medically controlled: basal cell carcinoma of the skin, squamous cell carcinoma of the skin, carcinoma in situ of the cervix, and carcinoma in situ of the breast
20. Part 2 Only: The time since the last dose of prior IDH inhibitor treatment is within 30 days prior to the first day of study drug administration

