9.1.1 Statistical Hypothesis

No formal hypothesis testing is planned for this study. For efficacy endpoints, the study will provide estimates and associated 95% confidence interval (CI) for precision.

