Section 4.1.1 – Part 1 (Dose Escalation), Section 6.2.1.4 – Replacement of Patients, and Section 9.1.2.1 – Dose Escalation Part	
The language discussing whether patients who are not dose-limiting toxicity (DLT)-evaluable in a dose cohort “will” be replaced was updated to “may” be replaced.
	The language update is to reflect the possibility that not all non-DLT-evaluable patients may be replaced.
Section 5.1.1.3 – Rescreening	
Language and section were added to provide the possibility to rescreen patients who were unable to complete the procedures within the screening window, screen failed, or became eligible as the
	The addition of rescreening language was to provide clarity and guidance on patient rescreening.

Section Number	Summary of Change	Rationale for Change
	result of an amendment, status change, or change in extenuating circumstances.	
Section 5.2 – Inclusion Criteria; Part 2	
Language was added to “b” to clarify that patients with AML must have received at least 1 prior lines of therapy for their hematologic malignancy.
 
Language was added to “e” to clarify the number and acceptable prior lines of therapy.
 
Inclusion criterion 6 was added to indicate that patients with AITL must have measurable lesion as defined in Lugano 2014.
	
The updates to “b” and “e” were to clarify the number of lines of therapy and acceptable prior lines of therapy for each population.
 
The addition of inclusion criterion 6 was to clarify the requirement of measurable lesions for patients with AITL.

Section 5.3 – Exclusion Criteria	
Language for criterion 8 was updated to exclude patients with congenital long QT syndrome.
 
Language for criterion 9 was updated to exclude patients with electrocardiogram results showing no clinically significant findings and a QTcF interval of >470 ms for women and >450 ms for men.
	
The language updates were made per regulatory request.

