Section 5.2 – Exclusion Criteria #17, #18, #19	
Added exclusion criteria #17, #18, and #19, respectively:
 
Subjects with a medical condition, physical examination finding, or clinical laboratory finding that, in the Investigator's opinion, contraindicates the use of an investigational drug or that may affect the interpretation of the results or renders the patient at high risk from treatment complications.
 
Subjects with a known hypersensitivity to HMPL-306 or to any of its excipients.
 
Subjects with presence of second primary malignant tumors within the last 2 years, with the exception of the following, if medically controlled: basal cell carcinoma of the skin, squamous cell carcinoma of the skin, carcinoma in situ of the cervix, and carcinoma in situ of the breast.
	Request by Health Authority
Section 6.1.10.4 – Blood Chemistry	Revised to add blood glucose as part of the safety monitoring tests.	Request by Health Authority
Section 6.2.1.1 – Permanent Discontinuation of Treatment	Revised language for subjects that would be discontinued from treatment from "may be discontinued" to "could be discontinued" and added reference to Table 9, Table 10, and Table 11.	Request by Health Authority
Section 6.2.2 – Study Stopping Rules	Revised language to clarify that if the study is halted as per Stopping Rules in either the dose escalation part or the dose expansion part, the study will only be restarted after Regulatory Approval as per local regulations.	Request by Health Authority
Section 11.1.1 – Safety Review Committee	In Section 6.2.2, clarified that the provided dose stopping rules common to both dose escalation and dose expansion parts are applicable to individual subjects.	To improve clarity
Appendix 1 – PK/PD/Biomarker/ECG Assessments for Escalation Cohorts Appendix 2 - PK/PD/Biomarker/ECG Assessments for Expansion Cohorts	Revised to include an ECG at screening in order to confirm eligibility.	Request by Health Authority
	Revised to include blood and bone marrow samples for gene mutation analysis at cycle 2 day 1 (C2D1). Updated table title to include PK/PD/Biomarker/ECG assessments for escalation and expansion cohorts	To improve clarity
	Updated footnote 1 to add "Pre-dose bone marrow sample collection should be performed within 24 hours prior to	A 24-hour pre-dose window was added to provide sufficient flexibility in the clinic to

Section Number	Summary of Change	Rationale for Change

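### The ECG-findings clause of exclusion criterion 9 is worded as an inclusion requirement, so as printed it misses a clinically significant ECG finding when QTcF is within limits

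*Protocol*

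**What the plan says.** The lead-in to Protocol Section 5.3 makes every listed item an exclusion: "Patients are not eligible for enrollment into this study if they meet any of the following criteria". Criterion 9 has three clauses under that lead-in:

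- **ECG findings:** "Electrocardiogram without any clinically significant findings, and for QT interval corrected for heart rate".
- **QTcF and other factors:** "interval >470 ms (for women) and >450 ms (for men), or other factors that increase the risk of QT prolongation or arrhythmic events". The last of these is subject to the investigator's assessment.

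The Amendment 4 entry in Appendix 18 describes the same change: "Language for criterion 9 was updated to exclude patients with electrocardiogram results showing no clinically significant findings and a QTcF interval of >470 ms", with a corresponding 450 ms figure for men. The log is cited only to show that the negation was in the sponsor's own text and did not arise when the PDF was read.

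The criterion is in active use. Appendices 1 and 2 schedule a screening ECG, and the Amendment 2 log gives the reason: "Revised to include an ECG at screening in order to confirm eligibility". Section 5.2 contains no ECG requirement that could carry the intended meaning instead.

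**The concern.** An ECG without significant findings is normally something a patient must have in order to enter a trial. Here it sits in a list where meeting an item means being turned away. The other two clauses of the same sentence are worded as exclusions, so the sentence points in two directions.

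Three features of the plan make the wording matter:

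- ECGs are named among the primary safety endpoints in both parts (Protocol Section 3), and QTcF drives the treatment rules in Section 7.5.3.
- Section 5.1 defines an enrolled patient as one found eligible with no waiver of population criteria, and Section 11.2.1 requires full verification of adherence to the eligibility criteria. Sites and monitors therefore have to apply this sentence as a test.
- SAP Sections 3.2 and 5.2.2 provide for deviations to be reviewed before database lock and for major ones to be summarized. A criterion with two readings cannot be audited consistently.

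**Working it through.** The plan gives no figure to reproduce, and no statistical input is involved: "No formal hypothesis testing is planned for this study". The check is a truth table on the sentence.

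**Inputs, all from criterion 9**

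- S: the ECG shows a clinically significant finding.
- Q: QTcF is above the limit for the patient's sex.
- F: another factor raises QT or arrhythmia risk, in the investigator's assessment.

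**Reading A, the conjunction taken literally.** Excluded = (not S and Q) or F.

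**Reading B, each clause a separate exclusion.** Excluded = (not S) or Q or F.

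If F is present, both readings exclude. With F absent:

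| S | Q | Reading A | Reading B |
|---|---|---|---|
| no | no | not excluded | excluded |
| no | yes | excluded | excluded |
| yes | no | not excluded | not excluded |
| yes | yes | not excluded | excluded |

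**Results**

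1. A significant finding with QTcF within limits (third row) is not excluded under either reading. This does not depend on how the clauses are joined.
2. Under Reading A, a significant finding together with long QTcF (fourth row) is also not excluded, although the same QTcF with an otherwise unremarkable ECG is.
3. Under Reading B, a normal ECG (first row) is an exclusion.
4. The two readings disagree in two of the four rows, the first and the fourth.

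**Do other criteria fill the gap?**

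- Criterion 8 is confined to "Patients with congenital long QT syndrome or a known history of severe and/or uncontrolled ventricular arrhythmias".
- Criteria 5, 6 and 7 cover advanced heart failure or low ejection fraction, recent myocardial infarction, and unstable or uncontrolled angina.
- Criterion 10 covers QT-prolonging medication.
- Criterion 17 is a catch-all that depends on the investigator's opinion. It begins "Patients with a medical condition, physical examination finding, or clinical laboratory finding that" and does not name ECG findings.

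These overlap with part of the third row. None of them states an ECG-findings rule or changes how criterion 9 reads.

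**The case against.** The best counter-argument is about scope and consequence, and most of it stands.

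- **Only one of three clauses is negated.** A reader might infer that criterion 9 lets in abnormal ECGs generally. The text does not support that. Long QTcF is excluded on both readings when there is no other significant finding, and the other-factors clause excludes on its own terms. A significant finding that the investigator regards as an arrhythmia risk could also be caught there.
- **A reader might equally infer that the protocol bars every patient with a normal ECG.** That follows only from Reading B, and a site would hardly apply it.
- **There are backstops.** Criteria 5 to 8 and 10 exclude specific cardiac conditions and QT drugs. Criterion 17 is discretionary, but deciding whether an ECG finding is clinically significant also takes judgement, so the practical gap is narrower than the literal one. On-treatment QTcF rules and triplicate ECGs apply regardless of the eligibility wording.
- **No harm is shown.** The documents report no disagreement between site and monitor, and no patient enrolled through the gap.
- **Enrolment may be over.** SAP Section 1 describes enrolment in the past tense, and the footnote to SAP Table 13 says only one patient entered Part 2 Cohort A.

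These points limit the consequence. They do not make the sentence correct: the third row of the table stays outside criterion 9 under both readings.

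**Conclusion.** The first clause of criterion 9 is wrong as written. Criterion 9 does not exclude a patient who has a clinically significant ECG finding, QTcF within limits and no other QT or arrhythmia factor. What happens to a significant finding with long QTcF, or to a normal ECG, depends on which reading is taken. This is a drafting inconsistency and not a debatable design choice.

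The effect is on eligibility decisions and on how deviations are classified. It is not numerical: no estimate, interval or sample size depends on it. The documents do not allow a count of affected patients, and none is assumed.

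The conclusion rests on two assumptions: that the lead-in governs criterion 9 as it does every other item, and that the other-factors clause stands on its own and is not tied to the ECG-findings clause. The documents do not support the stronger inference that unsuitable patients were actually enrolled.

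**What to change.** Reconcile the ECG-findings clause, the QTcF clause and the Section 5.3 lead-in so that all point the same way and each clause has one reading. Rewording the clause as an exclusion, or moving it to Section 5.2 as a requirement, would each resolve the conflict; the choice is the sponsor's. No QTcF limit or other clinical threshold is questioned or proposed.

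If enrolment is still open, the cost is a one-sentence protocol correction. If it is closed, a short clarification memo should record the reading that sites actually applied, and that reading should be used when eligibility deviations are reviewed and classified before database lock. Neither route changes the planned analyses.

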6 STUDY CONDUCT

Recruitment is estimated to take approximately 18 months. The estimated duration for the entire study from the time the study is open to enrollment until completion of data analyses is approximately 36 months. During the study, assessments at each study visit will be performed as listed in [Table 1](#) and [Table 2](#) as described in this section.

6.1 Study Procedures

If there is dosing on assessment day, all assessment examinations must be completed before study drug administration, except for 12-lead electrocardiogram (ECG), ECHO/MUGA scan, ophthalmologic examination, and efficacy assessments.

6.1.1 Study Drug Administration

6.1.1.1 Dose Escalation

A single dose of HMPL-306 will be administered on Day 1 of PK week (Section [6.1.2](#)) for each cohort in the dose escalation part. After PK week, all patients will receive continuous, daily administration of HMPL-306 beginning at C1D1.

